6.8.3 Holman Index >0.4

Patients with Holman index >0.4 will be considered as biochemical EFAD. It will be confirmed in the context of low LA, low ARA, and high eicosatrienoic acid (Mead acid).

Clinical EFAD is diagnosed in the presence of any clinical features of EFAD (dermatitis, diarrhea, perianal irritation, growth and development failure, recurrent infections, irritability, and/or poor wound healing).

The management of these patients includes the assessment, the record, and the increase of LA intakes until the Holman Index normalizes and clinical features, if present, disappear.

The daily monitoring of LA intakes, and the approximately every 15 day monitoring of LA and ARA levels and Holman Index will persist until the Holman Index normalizes and clinical features disappear. If the Holman Index does not reduce to <0.4 or if it continues to increase, lipid intake will be further increased. The amount of the increase in LA intake should be determined by the clinician considering the clinical state of the patient and the safety of increasing the total lipid intake.

Some patients may have higher requirements for EFAs due to an underlying disease (e.g. high demand for growth and wound healing). Total parenteral lipid intake should usually remain below the maximum intake (Table 4, Dosing Schedule), which is an amount that is normally adequate for prevention of EFAD in all patients. The patient should receive the increased LA intake for at least 1 week prior to repeating the FA profile with the Holman Index assessments to allow time for the physiologic effects of the FA to occur.

When EFAD persists despite maximal lipid intake, the ILE should be unblinded. If the patient is receiving Clinolipid, the patient should be switched to Intralipid to allow for greater delivery of LA.

Additional LA intakes may be supplied via intravenous and/or enteral/oral routes.

If severe hypertriglyceridemia (triglycerides >400 mg/dL) develops, the cause should be investigated. If it is determined to be related to the ILE, lipid intake may be adjusted using the ILE with the higher relative content of LA.

If direct bilirubin increases above 2.5 mg/dL suggestive of cholestasis, a reduction of total lipid intake may be considered while continuing to provide adequate LA. The adequacy of LA intake needs to be confirmed by the unblinded pharmacist(s).

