6.8.4 Holman Index >0.4 at baseline

Some study patients (especially premature infants) may demonstrate FA profile and Holman index compatible with EFAD at baseline due to their limited fat stores. The treatment for these infants is to administer EFA via ILE as part of their PN as described in Table 4, Dosing Schedule and being sure to reach the maintenance dosage. Infants with EFAD at baseline are to be followed regularly (approximately every 15 days) while receiving ILE per study protocol for improvement in their FA profile and Holman Index.

• If the Holman Index does not decrease with lipid administration in accordance with Table 4, Dosing Schedule, the patient may have greater than normal

requirements for EFA and the LA intake should be increased to the maximum dosage according to Table 4, Dosing Schedule and at the investigator's discretion.

- If the patient still does not respond, the investigator will be unblinded to determine if the patient is receiving Clinolipid or Intralipid. If the patient is receiving Clinolipid, the patient should be switched to Intralipid (as Intralipid contains a higher concentration of LA than Clinolipid).
- If the patient does not respond to Intralipid at maximal lipid dosage, consider increasing the LA intake with an enteral/oral source of LA or some additional intravenous Intralipid intakes.

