6.14 Removal of Patients from the Study/ Discontinuation of the Study

Any patient/legal representative may voluntarily withdraw consent for continued participation and data collection at any time during the course of the study. The Investigator may terminate a patient's study participation at any time during the study if the Investigator judges it to be in the patient's best interest.

Patients may be withdrawn or prematurely discontinued from the study treatment/assessments for any of the following reasons:

- Adverse Event(s)
- Clinically significant change in a laboratory parameter
- Protocol violation (i.e. patient failed to meet protocol entry criteria or did not adhere to the protocol requirements)
- Pregnancy
- Patient or any legal representative requests to withdraw from the study
- Sponsor or Investigator terminates the study

All patients randomized to Clinolipid who must receive Intralipid for rescue therapy purposes will be discontinued from the trial.

Parenteral nutrition therapy may be interrupted and restarted (based on the initial randomization) within a 1 to 2-day window, subject to adjudication from the medical monitor who conducts a clinical review of current patient status, assessment of any potential AE/SAEs, discussion/clarification with the investigator to resume or abort study treatment. The outcome of the adjudication process will not preclude the monitoring for AE/SAEs for the subsequent 30 days and in the event of an AE, following the subject until the AE resolves, stabilizes or the subject returns to baseline. If there is a likelihood that the patient will require restart of PN within 1 to 2 days of the initial stoppage, then it is recommended to delay performing the End of Study Treatment procedures. However, the End of Study Treatment procedures should be completed within 2 days of the initial stoppage if the patient has not restarted PN, as per Section 7.2.4 and Appendix 1 Schedule of Events.

If a patient's participation is discontinued, the reason(s) must be recorded in the source documents and in the CRF.

End of study treatment procedures should be performed when a patient withdraws or is discontinued from the study.

Patients who are withdrawn from the study will not be replaced.

The study may be discontinued:

- If new safety information becomes available indicating that continuing the study treatment or procedures may jeopardize the safety of the patients
- Because of an administrative decision by the Sponsor

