9.3 Analysis Populations

The analysis sets in this study include: the Full Analysis Set (FAS), the Per Protocol Set (PPS), and the Safety Analysis Set. The FAS includes all patients who are randomized to receive either Clinolipid or SOC SO-based lipid emulsion (Intralipid), consistent with the intention-to-treat principle. The PPS includes a subset of patients in the FAS who have Holman Index measurements taken at baseline and at least 1 other time point postbaseline, who have received a minimum of 7 days of ILE treatment, and are without a major protocol violation (i.e. violation that potentially impacts the primary endpoint). The Safety Analysis Set includes all patients that have received treatment (Clinolipid or SOC).

Subgroup analyses of patients by age group (e.g., premature infants born <37 weeks of gestation up to 1 month CA, full-term neonates born \geq 37 weeks of gestation <1 month of age, infants 1 to <12 months of age, children 1 to <10 years of age, adolescent 10 to <18

years of age) and subgroup analyses for neonates according to GA and BW will be conducted.

The primary endpoint analysis and secondary endpoint analyses of liver disease including parenteral nutrition-associated liver disease (PNALD) and the adequacy of nutritional intervention will be conducted for both the FAS and PPS. All safety analyses will be conducted on the Safety Analysis Set.

Infants found to subsequently have baseline EFAD will not be considered to have treatment emergent EFAD and will be analyzed separately from infants with normal baseline EFAD status. Unblinded infants will be analyzed separately as well.

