1.5.1 Definition of Analysis Populations

Full analysis set (FAS): all patients who are randomized to receive either Clinolipid or standard of care soybean oil-based lipid emulsion (Intralipid) and have received at least one randomized study treatment. This dataset will follow the intent-to-treat principle and will analyze patients by planned randomized arm.

Per protocol set (PPS): all patients in the FAS who have Holman Index measurements taken at baseline and at least 1 other timepoint post-baseline, who have received a minimum of 7 days of ILE treatment, and are without a major protocol violation (i.e. violation that potentially impacts the primary endpoint).

Deviations that could be considered for exclusion in a PP analysis

- Randomization or treatment errors
- Investigational product not handled properly
- Key exclusion criteria such as:
 - Patients with liver disease including cholestasis
 - Patients with severe hyperlipidemia or severe disorders of lipid metabolism
 - Patients who are unable to tolerate necessary laboratory monitoring
 - Patient requires or is expected to require propofol for sedation

Deviations that should **not** lead to exclusion of data in a PP analysis

- Patients who violate inclusion/exclusion criteria relating to patient safety
- Missed informed consent signature/date
- Any deviation that does not directly impact the primary endpoint

Safety analysis set (SS): the set of all patients who have been administered study treatment (Clinolipid or Intralipid). Patients will be analyzed according to treatment received.

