3. CHANGES FROM ANALYSIS PLANNED IN PROTOCOL

There are no planned changes in analyses from the protocol.

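### Protocol 9.3 sets unblinded infants apart although persistent EFAD triggers unblinding; the SAP does not, yet declares no change, so two primary EFAD figures are defensible

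*Protocol*

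**What the plan says.** Protocol 9.3 defines the FAS as all randomised patients under intention-to-treat and runs the primary analysis on the FAS and PPS. It then adds two carve-outs. The first concerns infants who already had EFAD at entry: "Infants found to subsequently have baseline EFAD will not be considered to have treatment emergent EFAD", and they are analysed apart from infants with normal baseline status. The second follows at once: "Unblinded infants will be analyzed separately as well".

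Unblinding is tied to EFAD in two places. For on-treatment EFAD, Protocol 6.8.3 says "When EFAD persists despite maximal lipid intake, the ILE should be unblinded". For EFAD present at baseline, Protocol 6.8.4 says "If the patient still does not respond, the investigator will be unblinded to determine if the patient is receiving Clinolipid or Intralipid". Both apply to either arm. Protocol 6.14 adds a consequence for one arm only: "All patients randomized to Clinolipid who must receive Intralipid for rescue therapy purposes will be discontinued from the trial".

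The SAP says of the FAS (1.5.1): "This dataset will follow the intent-to-treat principle and will analyze patients by planned randomized arm". SAP 2.4.1 makes the FAS the primary set with the PPS as support. SAP 2.4.1.1 counts a patient as an event for any Holman Index above 0.4 during study treatment, dated at the first occurrence. It makes no exception for unblinding or for baseline EFAD, and the table list in the SAP appendix has only FAS and PPS versions of the EFAD tables. SAP section 3 states: "There are no planned changes in analyses from the protocol".

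**The concern.** Unblinding happens after randomisation and, on the 6.8.3 route, because the primary outcome occurred and did not resolve. A rule that sets unblinded infants apart therefore selects on the outcome. An infant whose EFAD resolves stays in the main count, while one whose EFAD persists may leave it. The rule names infants only, so an older child with the same course would stay.

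The study is descriptive, and the EFAD risk in each arm is its main product. If an analyst can report the risk with or without the persistent cases, and cite a governing document for either, the primary result is not fixed before the treatment codes are opened.

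**Working it through.** The documents state no EFAD rate, power or target difference, and the sample size of 100 rests on feasibility, so there is no planned figure to reproduce. The check is one of reading, followed by an illustration.

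**1. What the 9.3 sentence can mean.**

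- *Left out of the main result.* The sentence carries on from the baseline-EFAD rule, which does take infants out of the treatment-emergent count. This is the natural reading. It removes 6.8.3 cases among infants.
- *Shown additionally.* The infants stay in the FAS result and also appear in a separate display. No case is lost, but the SAP then omits an analysis that the protocol specifies.
- *Only the baseline-EFAD infants unblinded under 6.8.4.* These are already not treatment-emergent cases, so no incident case is lost. Again the SAP has no such analysis.

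**2. What the SAP does.** On the 6.8.3 route the first value above 0.4 necessarily comes before unblinding. Under SAP 2.4.1.1 that first date is the event, so later unblinding, product switch or discontinuation does not erase it. The SAP also departs from the baseline-EFAD rule: an infant with EFAD at entry who is still above 0.4 on treatment is an event under SAP 2.4.1.1 but not under Protocol 9.3.

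**3. Direction of the bias on the first reading.** With x EFAD cases among n patients, and u of those cases unblinded and set apart:

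- all kept: x/n
- set apart: (x − u)/(n − u)
- fall: u(n − x) / [n(n − u)], which is positive whenever u ≥ 1 and x < n.

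The risk in an arm can only go down.

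**4. Illustration.** n = 50 per arm is the planned number. The event and unblinding counts are assumptions. All unblinded cases are taken to be infants without baseline EFAD, and every patient is taken to have a post-baseline Holman Index.

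| EFAD cases (Clinolipid, Intralipid) | Unblinded | All kept | Set apart | Difference, points |
|---|---|---|---|---|
| 3, 1 | 1, 0 | 6.0% vs 2.0% | 2/49 = 4.1% vs 2.0% | 4.0 → 2.1 |
| 5, 1 | 2, 0 | 10.0% vs 2.0% | 3/48 = 6.25% vs 2.0% | 8.0 → 4.25 |
| 8, 2 | 4, 1 | 16.0% vs 4.0% | 4/46 = 8.7% vs 1/49 = 2.0% | 12.0 → 6.7 |
| 5, 5 | 2, 2 | 10.0% vs 10.0% | 3/48 = 6.25% in each | 0 → 0 |

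Check of the formula on the second row: 2 × 45 / (50 × 48) = 3.75 points, which is 10.0 − 6.25.

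In the first three rows the Clinolipid risk falls by about 2 to 7 points and the arm difference is roughly halved. In the balanced row the difference is unchanged, but each risk falls by 3.75 points.

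**The case against.** The best defence is that the SAP governs the detail, as Protocol 9.1 says, and already keeps these patients. Protocol 9.3 itself calls the FAS intention-to-treat, and Protocol 9.5 divides by the total number of patients in the group. A separate display alongside the FAS result fits all of that. The narrower meaning is also arguable: 6.8.4 speaks of infants, as the disputed sentence does, whereas 6.8.3 speaks of patients.

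Much of this stands. Removal is one reading of an ambiguous sentence, and under the SAP as written no unblinded case is lost. It does not dispose of the point, for three reasons. Membership of the FAS is no guarantee of being counted, since baseline-EFAD infants are in the FAS too and 9.3 still separates them. If only 6.8.4 infants were meant, the sentence would add little to the one before it. And the SAP does not withdraw the rule, because it declares no change.

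A reader might go further and infer that the worst cases will be removed, mostly from the Clinolipid arm, and that EFAD is the only route to unblinding. The documents do not support that:

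- Both EFAD triggers apply to either arm, and no EFAD rate by arm is given. Clinolipid has about one third of the linoleic acid (18.6% against 54.7%; 18.6/54.7 = 0.34), which makes an excess plausible but does not show it.
- The Clinolipid-only rule in 6.14 is discontinuation after rescue, not unblinding.
- Other routes may exist. For ILE-related hypertriglyceridaemia, 6.8.3 allows adjustment with the emulsion richer in linoleic acid, which seems to require knowing the product. In one branch 6.8.2 says the investigator may remain blinded, which suggests that other branches may differ.

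**Conclusion.** The point holds as an unresolved conflict between protocol and SAP over which patients count in the primary result. It is not a demonstrated bias in the planned FAS analysis. On the natural reading of 9.3, an exclusion that depends on the outcome lowers the EFAD risk. Under the SAP it does not arise, but then the protocol's separate analyses of unblinded and baseline-EFAD infants have been dropped without being declared.

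The size depends wholly on assumed counts: about 2 to 7 points on the Clinolipid risk when 1 to 4 of 50 patients are set apart. The arm difference shrinks only if unblinding is more frequent on Clinolipid. These shifts are smaller than the sampling uncertainty in 50 patients (the exact 95% interval for 5/50 is 3.3% to 21.8%). Unlike sampling error, though, the shift in each arm's risk always goes the same way, and it can be prevented by wording. It should be settled before treatment codes are released.

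**What to change.** Replace the last sentence of Protocol 9.3, and carry the same rule into SAP 1.5.1 and 2.4.1.1, along these lines:

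> A patient of any age without EFAD at baseline who has a first on-treatment Holman Index above 0.4 counts as an event in the randomised arm in the FAS at that first date, whether or not the patient is later unblinded. Data after unblinding or product switch are flagged. Any separate summary of unblinded patients is supplementary. The number of patients unblinded is reported by arm.

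The restriction to patients without baseline EFAD is needed. Without it, 6.8.4 infants would become events, against the preceding sentence of 9.3. Align SAP 2.4.1.1 with that sentence so that baseline EFAD is not counted as treatment-emergent, and say whether those patients stay in the denominator. Protocol 9.3 names infants only, so state that the rule covers all ages. Record the difference from the protocol in SAP section 3.

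The cost is a few sentences in each document, a flag for the date of unblinding or switch, and one count per arm. On the 6.8.3 route the first qualifying value precedes unblinding, so no new data are needed. No dosing, rescue, unblinding or discontinuation rule changes.

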9.4 Demographics and Baseline Characteristics

Continuous demographic and baseline variables will be summarized using number of patients, mean, standard deviation, median, minimum, and maximum for each treatment group. Some variables such as sex, race, ethnicity, and age will be categorized and summarized by reporting the number and percentage of patients in each category for each treatment group.

9.5 Primary Endpoint

The primary endpoint is the risk of developing EFAD defined as defined by Figure in Appendix 3.

- The risk of developing EFAD in pediatric patients will be summarized by treatment group as frequency and percentage. Time to developing EFAD will be analyzed using the Kaplan-Meier approach.
- Both incidence rate and proportion of EFAD will be computed for each treatment group.
- The incidence rate of EFAD will be computed as the number of patients who develop EFAD during the Study Treatment Period divided by the corresponding person time (i.e. "person-day" which is computed as "total number of patients" times "treatment exposure period [day]" in the corresponding treatment group), and reported as per 100 patient days.
- The proportion of EFAD will be computed as the number of patients who develop EFAD during the Study Treatment Period divided by the corresponding total number of patients.

- The Holman Index will be summarized with descriptive statistics (number of patients, mean, standard deviation, median, minimum, and maximum) on an approximately 15-day basis in each of the 2 treatment groups (Clinolipid vs Intralipid).
- FA profiles will be summarized using descriptive statistics (number of patients, mean, standard deviation, median, minimum, and maximum) in each of the 2 treatment groups (Clinolipid vs Intralipid), as well as descriptive statistics of genetic polymorphisms in the FADS1 and FADS2 genes.

9.6 Secondary Endpoint(s)

The three secondary endpoints of the study include 1) the development of liver disease including PNALD; 2) the adequacy of nutritional intervention; and 3) the safety profile including AEs, SAEs and AESIs.

9.6.1 Liver Disease, Including Parenteral-Associated Liver Disease

9.6.1.1 Parenteral Nutrition-Associated Liver Disease

The risk of developing PNALD in pediatric patients by treatment will be summarized as frequency and percentage, as well as time to developing PNALD using the Kaplan-Meier approach. Both incidence rate and proportion of PNALD will be computed for each treatment group.

The incidence rate of PNALD will be computed as the number of patients who develop PNALD during the Study Treatment Period divided by the corresponding person time (i.e. "person-day" which is computed as "total number of patients" times "treatment exposure period [day]" in the corresponding treatment group), and reported as per 100 patient days. The proportion of PNALD will be computed as the number of patients who develop PNALD during the Study Treatment Period divided by the corresponding total number of patients.

9.6.1.2 Hepatic Integrity

Hepatic integrity (ALP, AST, ALT, GGT, total and direct bilirubin) will be evaluated by presenting descriptive summary statistics (number of patients, mean, standard deviation, median, minimum, and maximum) at different measurement time points from baseline to end of study treatment during the study period in each of the 2 treatment groups (Clinolipid vs Intralipid).

Each hepatic integrity parameter will also be summarized in shift tables comparing end of study treatment and maximal values during the study intervention with those at baseline (mean, standard deviation, median, minimum, and maximum) including the delay (days) between baseline and maximal value in each of the 2 treatment groups (Clinolipid vs Intralipid). Shift categories will include normal and abnormal (>1 to 3 and >3-fold the upper limit of normal range). In addition, assessment for drug-induced liver injury (DILI) will be conducted according to Hy's Law and eDISH criteria,^{1,2} with additional detail included in the SAP.

9.6.1.3 Plasma Phytosterol, Cholesterol, and Squalene Levels

Plasma phytosterol, cholesterol, and squalene levels will be summarized using descriptive statistics (mean, standard deviation, median, minimum, and maximum) at baseline and the end of study treatment, as well as maximal value during the study and the delay (days) between study baseline and maximal value in each of the 2 treatment groups (Clinolipid vs Intralipid). In addition, the correlations between plasma phytosterol levels and direct bilirubin values will be assessed by computing a Pearson's correlation coefficient or a Spearman correlation coefficient depending on whether the normality assumption is fulfilled.

9.6.2 Adequacy of Nutritional Interventions

9.6.2.1 Nutritional Intake

Prescribed and actual nutritional intake (fluid, energy, protein, carbohydrates, and lipids) from parenteral and enteral nutrition will be collected and recorded daily. They will be summarized on a daily basis during the first 2 weeks of treatment and on a 15-day basis afterwards up to end of study treatment for each of the treatment groups.

9.6.2.2 Growth

Weight at baseline and during treatment will be assessed daily and will be summarized on an approximately 15-day basis using descriptive summary statistics in each of the treatment groups.

Length or height (and head circumference for infants <1 year of age) will be assessed and summarized at baseline and approximately every 15 days up to end of study treatment using descriptive summary statistics (number of patients, mean, standard deviation, median, minimum, and maximum in each of the 2 treatment groups (Clinolipid vs Intralipid).

Growth will be assessed and evaluated from baseline to end of study treatment on an approximately every 15-day basis using descriptive summary statistics in each of the treatment group as follows:

- Gain in weight (g/kg/day in infants <1 year of age, g/day in children and adolescents) and gain in length/height (mm/week in all) and head circumference (mm/week in infants <1 year);
- Changes in the SDS from reference growth curves (Fenton growth curve for premature infants, WHO growth standards for infants and children ages 0 to 2 years, or CDC growth charts for children age ≥2 years)

